4.0 Inclusion/Exclusion Criteria

Inclusion criteria for study participation will be:

- Intact cognitive status and ability to provide informed consent
- Ability to read and write in English sufficiently to understand and complete study questionnaires
- Age 18-55 inclusive
- Presence of persistent daily low back pain of at least three months duration and of at least a 3/10 in average intensity

Exclusion criteria will be:

- Engagement in > 2 days/wk and > 60 min/wk of moderate or vigorous intensity activity based on responses to 6 validated survey questions at screening (CDC BRFSS), and confirmed by exercise-specific questions in the electronic diary obtained prior to the exercise intervention period
- History of renal or hepatic dysfunction
- Current or past alcohol or substance dependence
- A history of PTSD, psychotic, or bipolar disorders
- Chronic pain due to malignancy (e.g., cancer), autoimmune disorders (e.g., rheumatoid arthritis, lupus), or fibromyalgia
- Recent daily opiate use
- Use of any opioid analgesic medications within 72 hours of study participation (confirmed through rapid urine screening conducted prior to study participation)
- Females who are pregnant
- History of cardiovascular disease (including myocardial infarction)
- History of seizure disorder

- Prior allergic reaction/intolerance to morphine or its analogs
- Presence of cardiac disease or any other medical condition that would make engaging in the aerobic exercise manipulation unsafe

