6.0 Study Procedures

Screening/Consent visit (Day 1 of Study Participation): Potential participants will be screened to determine eligibility for participation in the study. This screening, supervised by the study physician, will include evaluation to characterize the nature of the chronic back pain and to confirm eligibility to engage in the exercise manipulation. Potential participants will also be screened for the exercise exclusion criteria by answering questions related to moderate-vigorous physical activity from the CDC Behavioral Risk Factor Surveillance Survey to classify potential subjects as active or inactive. Following informed consent, participants will complete study questionnaires. Questionnaires will include assessment of occupational status (Employed, Not Working, Disabled), and for working individuals, number of hours worked per week and nature of the job for use as an additional measure of activity. Participants will also complete the International Physical Activity Questionnaire (IPAQ) to gather additional relevant physical activity

information prior to beginning participation in the study, to supplement diary-based data regarding exercise activity. Questionnaires assessing factors related to back pain, anger, depression, anxiety, pain coping, and pain medication responses will be completed. Participants will then complete the 5-day pre-manipulation electronic diary assessment procedures.

Pre-Manipulation 5 day Electronic Diary Monitoring Period (Days 2-6): Daily chronic back pain intensity will be assessed for 5 days pre-manipulation via an electronic pain diary using handheld Palm® Zire 22 PDAs, running the Palm OS platform. To provide a representative sampling of daily back pain intensity, participants will be prompted by an audible alert at 9am and again at 6pm daily. At each prompting, participants will be asked to electronically record ratings of their current back pain, recent sleep, activity levels, and mood using 9 point numeric scales. Participants will begin the laboratory portion of the study following completion of this first diary monitoring period.

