Lab Visit 3: Participants will undergo a urine screening for opiate use (females will also be screened for pregnancy); 5 minutes of seated rest; participants rate their current low back pain intensity; nurse inserts i.v. cannula; nurse administers randomized drug dose #1. Administration of randomized drug dose #1 will be followed by 10 minutes of seated rest to achieve peak drug levels; participant rating of chronic pain intensity; thermal pain task #1; assess thermal pain intensity; assess drug side effects and psychoactive effects; nurse administers randomized drug dose #2. Administration of drug dose #2 will be followed by 10 minutes of seated rest to achieve peak drug levels; participant rating of chronic pain intensity; thermal pain task #2; assess thermal pain intensity; assess drug side effects and psychoactive effects; nurse administers randomized drug dose #3 . Administration of drug dose #3 will be followed by 10 minutes of seated rest to achieve peak drug levels; participant rating of chronic pain intensity; thermal pain task #3; assess thermal pain intensity; assess drug side effects and psychoactive effects; nurse administers randomized drug dose #4. Administration of drug dose #4 will be followed by 10 minutes of seated rest to achieve peak drug levels; participant rating of chronic pain intensity; thermal pain task #4; assess thermal pain intensity; assess drug side effects and psychoactive effects; seated rest until side effects remit.

Exercise Manipulation (Weeks 4 – 10 of study participation): Following the third laboratory visit, participants will be randomly assigned to study condition, stratified by recruitment source (clinic vs. community). Participants randomly assigned to the exercise condition will then complete the 18 session aerobic exercise manipulation supervised by an ACSM-certified personal trainer at the Dayani Center (3 exercise sessions per week for 6 weeks). Participants assigned to the control condition will not undergo any manipulation during this 6 week period, and will be asked to continue their current activity levels and not engage in any additional exercise activity during the study period (confirmed via electronic diary). All subjects will complete brief pain and psychosocial questionnaires once weekly by phone.

Lab Visits 4 – 6 (\approx Weeks 11-12): Identical procedures to those described above for Lab Visits 1-3. Drug order is again randomized and counterbalanced.

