Post-Manipulation 5 day Electronic Diary Monitoring Period (\approx Week 11, between Lab Visits 4-5): Identical to pre-manipulation electronic diary procedures described above.

Description of Laboratory Visit Procedures:

All laboratory procedures will be conducted with participants seated upright in a comfortable chair. Each participant's series of three laboratory sessions (placebo, naloxone, morphine) carried out both pre- and post-manipulation will be scheduled within an ≈ 10 day period, at the same time of day to control for variance due to circadian rhythms.

Study Drug Protocol: Study drugs will be administered (in double-blind fashion) in randomized, counter-balanced order. The assigned study drug will be administered within a given session over 4 infusions (2 min each) according to the following protocol, depending on the assigned drug for that visit: 1) 4 doses of saline placebo (20ml each), 2) an 8mg dose of naloxone (in 20ml saline vehicle), followed by saline, 4mg naloxone, and saline, or 3) morphine sulfate (0.03 mg/kg in 20ml saline vehicle initially, followed by 3 incremental doses of 0.02mg/kg each). To avoid excessive morphine doses (and increased side effect risks) for individuals who are obese, a modified weight adjustment will be employed for individuals more than 30% over ideal body weight based on subjects' observed weight in clinic compared to appropriate ideal body weight for males (50kg+2.3kg for each inch over 5 feet) or females (45.5kg +2.3kg for each inch over 5 feet) [from <http://www.globalrph.com/>]. For individuals meeting this obesity criterion, morphine dosage will be based on Adjusted Body Weight rather than actual body weight, as calculated by: $\text{Ideal Body Weight} + 0.4 (\text{actual weight} - \text{Ideal Body Weight})$.

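### The diary said to confirm that controls do not take up exercise is not scheduled on any of the 42 manipulation days, so control-arm exercise in that period is checked only indirectly and incompletely

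*Combined protocol and SAP*

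**What the plan says.** Section 6.0, under the exercise manipulation, tells controls to keep their current activity levels and "not engage in any additional exercise activity during the study period (confirmed via electronic diary"). The manipulation is headed "Exercise Manipulation (Weeks 4 – 10 of study participation") and lasts six weeks.

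The same section schedules the diary twice. The first is the "Pre-Manipulation 5 day Electronic Diary Monitoring Period (Days 2-6"), which precedes Lab Visit 1 and therefore randomisation. The second is the "Post-Manipulation 5 day Electronic Diary Monitoring Period", in about Week 11, "between Lab Visits 4-5): Identical to pre-manipulation electronic diary procedures described above".

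During the manipulation itself, the contact planned for both arms is the phone call: "All subjects will complete brief pain and psychosocial questionnaires once weekly by phone".

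On diary content, Section 6.0 lists "ratings of their current back pain, recent sleep, activity levels, and mood using 9 point numeric scales". Two other sections show that the diary also carries exercise items. Section 4.0 has the activity exclusion "confirmed by exercise-specific questions in the electronic diary obtained prior to the exercise intervention period", and Section 10.0 proposes exercise minutes from the post-intervention diary, recorded in both groups, as a possible covariate in the primary group analyses.

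**The concern.** The control condition consists of not exercising for six weeks, and participants know which arm they are in. Section 6.0 names one check on that abstention, and its schedule does not place the check in the weeks of exposure.

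Control-arm exercise would pull the group differences toward zero. Under Section 10.0, mediation is tested only for outcomes on which the exercise condition has a significant effect, so dilution could also stop the mediation tests from being run. If the result were null, the planned data could not tell an absent exercise effect from controls who had exercised. If it were positive, a statement that controls stayed inactive would rest mainly on five days after the manipulation.

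**Working it through.** **1. Diary coverage.** Count Week *w* as Days 7(*w*−1)+1 to 7*w*.

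| Window | Source | Days |
|---|---|---|
| First diary | Section 6.0 | 2-6 |
| Manipulation, within Weeks 4-10 | Section 6.0 | within 22-70; 6 × 7 = 42 days |
| Second diary, about Week 11 | Section 6.0 | 5 days within about 71-77 |

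There are 5 + 5 = 10 diary days, of which 0 fall in the manipulation. The week numbers are approximate, but the order is not: the first diary precedes Lab Visit 1, and the second follows Lab Visit 4, which comes after the manipulation.

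**2. Other instruments.**
- BRFSS activity questions: at screening (Sections 4.0 and 6.0).
- IPAQ: before participation begins (Section 6.0).
- Heart rate and exertion: during supervised sessions, so exercise arm only (Section 6.0).
- Weekly call: both arms and the right weeks, but no exercise item is named.
- Diary exercise minutes in the analysis: post-intervention diary only (Section 10.0).

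None is stated to record non-programme exercise during the manipulation.

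**3. The plan's power figures, reproduced.** Inputs from Section 10.0: n=116, two-sided 0.05, d=0.93 for exercise on EO function (the a path; studies range from 0.6 to 1.2), and b paths of r=0.27 (morphine response) and r=0.26 (back pain). Section 7.0 assigns half to exercise, so 58 per arm.
- r = d/√(d²+4) = 0.93/√4.8649 = 0.42, as stated.
- a path: noncentrality d√(58/2) = 0.93 × 5.385 = 5.01 on 114 df, power 0.999. This agrees with the stated figure of more than 0.90.
- Mediation: simulated bias-corrected bootstrap (4,000 replicates, 1,000 resamples, no direct effect) gives 0.805 for b=0.27 and 0.783 for b=0.26, against the stated 0.80.

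**4. Effect of dilution (hypothetical).** Let c be the share of the exercise contrast lost, so that the effect becomes d(1−c) with the SD unchanged. If a fraction f of controls gain a fraction g of the full effect, c = f × g. For example, c=0.20 needs 20% of controls gaining all of it, or 40% gaining half.

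| c | d=0.93: diluted d | Power | d=0.6: diluted d | Power |
|---|---|---|---|---|
| 0 | 0.930 | 0.999 | 0.60 | 0.893 |
| 0.1 | 0.837 | 0.994 | 0.54 | 0.822 |
| 0.2 | 0.744 | 0.978 | 0.48 | 0.727 |
| 0.3 | 0.651 | 0.935 | 0.42 | 0.611 |
| 0.5 | 0.465 | 0.700 | 0.30 | 0.360 |

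At d=0.93, power drops below 0.90 at about c=0.35.

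Mediation power with b=0.26 (3,000 replicates for c above 0) is 0.783, 0.796, 0.781 and 0.654 at c = 0, 0.2, 0.3 and 0.5. It is limited mainly by the b path, so it hardly moves until dilution is large. This simulation does not impose the precondition of a significant exercise effect.

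**The case against.** Four arguments on the other side carry weight.

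- **The check is not absent.** The instruction refers to the study period, which includes Week 11, and the diary then yields exercise minutes in both arms. A reader might infer that no check exists or that contamination could never be seen. The documents do not support that: controls who took up exercise and kept it up could be detected. Exercise that began and ended before Week 11 could not.
- **The call's items are not listed.** A reader might infer that it asks about nothing except pain and psychosocial matters. The text says only that such questionnaires are completed, so an exercise question may exist. If it does, the sponsor need only write it in.
- **Contamination is not shown to be likely.** Participants are screened for low activity, have daily back pain of at least 3/10, and controls are told not to add exercise. Matching the full effect would mean matching 18 supervised sessions that build to 30 minutes at 70-85% of heart rate reserve. Nothing in the documents supports a particular rate.
- **The power loss is limited at the planning effect.** At d=0.93, 30% dilution leaves the a path above 0.90, and mediation power, on which the trial is sized, is almost unchanged. A reader might infer that the trial is underpowered on this account, which the figures do not show. However, d=0.93 comes from acute exercise in healthy people, not from training in chronic back pain, so the d=0.6 column also deserves attention.

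What remains is the mismatch between the stated confirmation and its schedule.

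**Conclusion.** The point holds as a gap between a stated check and the schedule meant to deliver it. The diary covers 0 of 42 manipulation days, and no other listed instrument is stated to record non-programme exercise in that time. The Week 11 minutes are a partial, indirect substitute.

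The harm is mainly to interpretation, since a null could not be read against observed control-arm behaviour. The effect on power depends on an unknown dilution: small at d=0.93 up to 30%, but material at d=0.6, where 20-30% dilution lowers power from 0.893 to 0.727-0.611. These figures assume all 116 participants are analysed, 58 per arm, and a hypothetical c.

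Adjusting for the Week 11 minutes would not repair the gap. They describe the wrong weeks, and because they are measured after randomisation and may be affected by assignment, adjustment could remove part of the exercise effect.

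**What to change.** 1. Add the activity questions already used at screening, worded for the past week, to the planned weekly calls in both arms, with identical neutral wording.
2. In Section 6.0, name these calls, in place of the diary, as the confirmation of control-arm abstention.
3. Report non-programme exercise minutes by arm, descriptively.
4. Keep the as-randomised comparison primary, and remove the post-intervention exercise minutes from Section 10.0 as a possible covariate in the primary group analyses.

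An analysis using randomisation as an instrument for exercise minutes is not recommended. It needs minutes to be the only route from assignment to outcome, and the exercise arm also has trainer contact at 18 sessions.

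The cost is a few minutes on each of six calls already planned. Weekly questions about exercise may prompt slightly more activity in controls, which the neutral wording should limit. Weeks already completed cannot be recovered.

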7.0 Risks

There are several potential risks to subjects. First, subjects will experience brief, moderate intensity acute pain upon application of the thermal pain stimuli used for evaluation of acute pain responsiveness. However, subjects have total control over the duration of their exposure to this pain because they terminate the task by indicating when they have reached their tolerance limit. Previous research indicates that this task is safe, but to further maximize safety, individuals experiencing cardiovascular problems will be excluded from this study. Because subjects have total control over the duration of the task, its psychological impact is expected to be minimal.

Participants will experience very brief, mild pain upon insertion of a cannula (for study drug administration) during each experimental session. Insertion will be performed by a trained nurse or physician to minimize discomfort associated with insertion of the cannula. There is a risk of infection and local inflammation at the site of cannula insertion. Precautions will be taken to insure that such risks are minimized.

The medication used for opioid blockade, naloxone, is not an experimental or new drug, and is FDA-approved. Previous studies indicate that it is safe for individuals who are not opiate dependent, do not have liver disease, and do not have cardiovascular problems. Potential subjects experiencing these types of problems will be excluded from this study to insure a maximal level of safety with drug administration. Subjects taking daily opiates, even if not dependent, will also be excluded from the study to avoid precipitating minor withdrawal symptoms. In some individuals, naloxone may increase pain sensitivity to the acute pain tasks somewhat, but again, participants may terminate these tasks if they've reached their tolerance limit. Based on previous studies, naloxone is expected to have limited if any direct effects on clinical pain intensity among pain patients, and therefore, there appears to be little risk of exacerbating patients' chronic pain conditions. Even if such changes do occur, the brief half-life of naloxone (on average, approximately 60-80 minutes) insures that any pain exacerbation will be of short duration. With the exception of possible effects on pain sensitivity, naloxone is not known to be associated with other clinically significant effects in healthy individuals who are not opiate dependent or using daily opiates.

The other study drug, morphine, is an FDA-approved opioid analgesic with a very long history of use in standard clinical practice. It can produce dose-dependent side effects including sedation, somnolence, nausea, brief vomiting, euphoria, and respiratory depression. The cumulative dose to be used in the proposed study (0.09 mg/kg) will be weight adjusted, and represents a relatively low dose within the normal range of dosages used in standard clinical practice, representing a dosage only slightly larger than in our recent work (0.08 mg/kg; Bruehl et al., 2013). This should help limit any negative side effects. The half-life of morphine is approximately 2 hours, and study participants will be kept under observation in each study session until any side effects remit to the point where it is safe for them to leave unassisted. If morphine side effects are severe, these effects will be immediately reversed by administration of naloxone as determined appropriate by the study physician.

As part of this study, half of the participants will be randomly assigned to undergo a 6-week supervised aerobic exercise manipulation as described above. To maximize safety with this type of exercise, individuals with a history of cardiovascular disease are excluded from participating in this study. The intensity of this aerobic exercise training will start low but progressively increase over the 6-week intervention period. Safety and possible discomfort associated with these increases in exercise intensity will be minimized via close monitoring by a certified personal trainer of participant's heart rate, perceived exertion levels, and back pain intensity during exercise. Exercise intensity will be adjusted as appropriate to maximize the participant's level of conditioning while minimizing exacerbation of back pain. In addition, participants will be able to choose your preferred form of exercise from several available options.

In the event new information becomes available that may affect the risks or benefits associated with this study, participants will be notified so that they can make an informed decision whether or not to continue their participation in this study. There may be unknown or unanticipated adverse effects in addition to those listed.

8.0 Reporting of Adverse Events or Unanticipated Problems Involving Risk to Participants or Others

The PI and co-investigators will carefully monitor adherence to the study protocol on a regular basis via direct supervision, monitoring of obtained study materials, and regular study team meetings. All adverse events and unanticipated problems will be immediately communicated across the two study sites. Deviations from protocol will be immediately corrected, and if appropriate, will be reported to the IRB and the program officer at NIH/NIDA (sponsoring agency).

9.0 Study Withdrawal/Discontinuation

Subjects will be informed that they can withdraw for any reason from the study at any time without penalty. Subjects may be withdrawn from the study if the study physician determines that their medical condition makes their participation in the study unsafe. Upon withdrawal from the study, subjects will be compensated for their participation (prorated as appropriate).

10.0 Statistical Considerations

Given the project focus on testing indirect (mediated) effects of the aerobic exercise manipulation via EO enhancement (mediator) on CP intensity (Aim 1), morphine analgesic requirements (Aim 2), and associated abuse relevant subjective effects (Aim 3), the project is powered specifically for the proposed bias-corrected bootstrap mediation analyses. Empirical power estimates for this mediation analysis approach are available⁶⁴. The mediation analyses will test the mediation model presented in Figure 2 below. The power estimates below jointly take into consideration the effect sizes for the a and b paths in Figure 2. The effects of exercise on EO analgesia (a path) can be derived from 3 studies in healthy individuals reporting differences in pain sensitivity following acute exercise between placebo and EO blockade (naloxone) conditions^{55,68,74}.

Effect sizes ranged from $d=.6$ to $d=1.2$ in directions indicating that opioid blockade reduced post-exercise analgesia, suggesting that EO function partly mediated the effect of acute exercise on pain intensity. The mean effect size across these studies for the impact of EO mechanisms on exercise-related analgesia was $d= .93$ (equivalent to $r=0.42$). This effect size is key to initial analyses of Specific Aim 1. The proposed sample size will result in a power exceeding 0.90 for testing effects of the exercise manipulation on EO function (two-sided $p<.05$ significance criterion). Effect size estimates for the b path in the mediational model reflecting influences of EO function on morphine responses can be derived from our prior work, which indicated an average effect size of $r=0.27$ for associations between natural variations in EO function (opioid blockade effects) and analgesic responses to a single morphine dose across all pain measures and both laboratory evoked pain tasks¹⁸. Effect size for the b path reflecting influences of EO function on chronic back pain intensity can be estimated from Bruehl et al.²⁵, with an effect size of $r=0.26$ for associations between EO analgesic function in the laboratory and diary ratings of chronic back pain intensity (greater EO function was associated with lower daily back pain intensity). Given these effect sizes for the a and b paths in the mediation model, the total sample size for the proposed project was selected as $n=116$, resulting in a power of 0.80 (two-tailed $p<.05$ criterion for significance) for testing mediation effects hypothesized in Aims 1-3 using the proposed bootstrap approach (based on Fritz and MacKinnon⁶⁴).

Data Reduction and Analyses

Blockade effect variables reflecting EO function will be derived by subtracting evoked pain responses during placebo from comparable responses during opioid blockade (separately for pre-manipulation baseline [BL] and post-manipulation). Given no theoretical rationale for expecting dose response effects with repeated dosing for placebo or naloxone conditions, we will average over the 4 pain stimuli within each of these drug conditions (separately for pre- and post-manipulation sessions) as a means of reducing random measurement error in deriving blockade effects. Blockade effects will be derived such that larger positive values reflect greater EO analgesia. To reduce number of variables, a mean value of the standardized EO function variables (blockade effects) will be derived and will be used initially in analyses (as in Bruehl et al.¹⁸). Chronic pain intensity pre- and post-manipulation will be defined as mean chronic pain ratings during the respective electronic diary sampling periods. As manipulation checks, we will determine whether degree of spontaneous EO function pre-manipulation is correlated significantly with evoked pain sensitivity and chronic pain intensity at BL. Total number of exercise minutes recorded during the post-intervention diary monitoring period (obtained in both groups) will be explored as a potential covariate for use in primary group analyses.

Primary Analyses.

Aim 1: To determine whether an aerobic exercise manipulation increases EO activity in CLBP patients, and whether these EO changes mediate manipulation-induced reductions in evoked pain responsiveness and daily CP intensity. We will conduct Group (exercise, control) x Time (BL, post-manipulation) mixed design ANOVAs to determine whether evoked pain sensitivity and CP intensity decreased significantly in the aerobic exercise group only. We will also conduct Group (exercise, control) x Time (BL, post-manipulation) mixed design ANOVAs on EO function (blockade effect variables pre- and

post-manipulation) to determine whether EO function increased in the aerobic exercise condition only. We will then test whether group differences in pre- to post-manipulation EO changes mediate group differences in pre- to post-manipulation reductions in evoked pain responsiveness and CP intensity using the bias-corrected bootstrap mediation testing approach of Preacher and Hayes¹⁰⁰. This approach is statistically powerful and not dependent on any assumptions about the sampling distribution of the variables, and was used successfully in our recently published work¹⁸. Per Preacher & Hayes¹⁰⁰, the only precondition for testing mediation will be presence of an effect to be mediated (i.e., the exercise condition is associated with significantly greater reductions in evoked pain responses and CP intensity than the control condition). For any outcomes for which this precondition is met, bootstrap tests of mediation will proceed using the Indirect procedure for SPSS^{100, 101} (<http://www.afhayes.com/spss-sas-and-mplus-macros-and-code.html#sobel>) as in our recent work¹⁸. If the 95% CI for the indirect effect in a given model does not include zero, this will indicate that the hypothesized indirect (mediated) effect is significant at $p < .05$. In this case, a significant indirect path will indicate that the link between aerobic exercise condition and reduced evoked pain responsiveness or CP intensity is significantly mediated by exercise-related EO enhancements. Significant direct and indirect paths jointly for the same outcome will indicate partial mediation. A significant direct path in the absence of a significant indirect path will be interpreted as indicating that the effects of the exercise manipulation on that outcome are mediated via non-opioid mechanisms.

Aim 2: To determine whether the exercise manipulation is related to achieving analgesic targets at lower opioid analgesic dosages, and whether these changes in analgesic requirements are mediated by pre-post EO changes. We will calculate dose response curves (per Prentice¹⁰²) based on morphine condition evoked pain responses at the four incremental morphine dose levels (separately for pre- and post-manipulation). Based on results of our prior work¹⁸, a 25% reduction in pain sensitivity relative to pre-exercise placebo pain responses will be the target. The total dosage of morphine needed at pre-manipulation BL to achieve a 25% reduction in pain responses (based on the dose response curve) will be compared to the dose of morphine needed to achieve a 25% pain reduction at post-exercise. We will conduct Group (exercise, control) x Time (BL, post-manipulation) mixed design ANOVAs to determine whether the total morphine dose required to achieve 25% pain relief decreased significantly in the exercise group only. We will then use mediation analysis procedures as described above to test whether group differences in pre- to post-manipulation EO changes mediate group differences in pre- to post-manipulation reductions in morphine dosage required to achieve 25% relief. The only precondition for conducting these mediation tests will be that there is an effect to be mediated, i.e., the exercise manipulation significantly alters the morphine dosage required to achieve 25% pain relief.

Aim 3: To determine whether the exercise manipulation is related to achieving a 25% morphine-induced reduction in evoked pain responsiveness with fewer negative side effects and abuse-relevant effects, and whether these changes are mediated by pre- to post-manipulation EO changes. Aim 3 analyses will parallel Aim 2 except that side effects and abuse-relevant effects at the 25% pain reduction target will be the DV.

Secondary Analyses.

Secondary exploratory analyses will examine potential moderator effects of sex and BL EO function on effects observed in primary analyses. These analyses will test whether the direction and magnitude of Group effects and/or Group x Time interaction effects for DVs depend on the sex of the participant and/or on degree of BL EO analgesia. To illustrate, GLM procedures will be used to test for a significant Group x Time x BL EO function interaction effect for morphine dosage outcomes in Aim 2. If significant, simple effects will be used to test whether Group was related to changes in required morphine dosages from BL to post-manipulation differently for those low vs high in BL EO function. Within the exercise group only, we will also examine associations between exercise intensity (i.e., average number of minutes \geq target 70% HRR during sessions) and pre-post manipulation EO changes and changes in morphine responsiveness. Finally, we will test whether: a) BL depression and anxiety symptoms predict analgesic responses; b) the exercise manipulation reduces these symptoms; c) such changes contribute to manipulation-related changes in analgesic responses.

